Study Design	
This is a single-center study of the effectiveness of open- and closed-loop DBS paradigms in the treatment of chronic neuropathic pain disorders that are refractory to current treatment options (e.g. two or more pain medications from different classes, spinal injections).
 
Our primary objectives are to:
 
 1) Determine the neural correlates of increased pain states in patients with chronic pain in order to enable targeted DBS treatment 2) Provide pain relief with neural stimulation 3) Establish the efficacy of open-loop and closed-loop DBS paradigms. 
DBS electrodes will be inserted into regions of the brain related to pain processing. After implantation of electrodes, study patients will undergo three phases of assessment.
 
In phase 1, patients will undergo ambulatory monitoring (~6 months) of their pain states linked to recordings of local field potentials (LFPs) in pain-processing regions. Stimulation will not be enabled during this period. This phase will be conducted in both the outpatient office setting and the patient's home environment. Throughout this period, data will be analyzed to develop a predictive model of increased pain states and to guide precision DBS treatment.
 
In phase 2, we will determine the stimulation parameters that optimally reduce the level of pain for each patient, in clinic daily, for 1-2 weeks. We will then randomly assign patients to 3-week periods of stimulation ON / stimulation OFF. We anticipate this phase will last approximately 6 months and that stimulation will be conducted in the office as well as the home setting. Patients will be under close monitoring, with frequent in-clinic appointments.

	
In phase 3, we will determine differences in pain relief efficacy for at-home open-loop versus closed-loop stimulation parameters (single-blind study). Patients will be under close monitoring, with frequent in-clinic appointments.
 
In phase 1, if data of sufficiently high quality is collected before the 6 month phase period ends, and a predictive biomarker is found before the 6-month phase period ends, the patient can accelerate to the next phases of the study to help ensure a rapid positive clinical outcome. Similarly, the patient may accelerate from phase 2 to phase 3 before the 6-month period ends to ensure rapid positive clinical outcomes.

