In phase 1, patients will be implanted and undergo long-term ambulatory monitoring of their self-reported pain states along with recordings of LFPs from electrodes implanted in the cingulate and orbitofrontal paired regions (~6 months in duration, time period based on previous pain studies [2, 85], visits 6-10, approximately 1 visit per month, up to 10 visits, if needed). Neural activity from implanted electrodes will be simultaneously recorded, one lead per recording channel. During this time period, neural data in combination with pain state reports will be analyzed in order to identify biomarkers of the pain experience and develop a predictive model of increased pain. Importantly, although recruitment will only include patients who are treatment-resistant to pain medication, patients will likely be on medication regimens for pain relief. These will continue to be managed by the patient’s regular pain management team (i.e. will be independent of this study). We will closely monitor the medication regimen and any changes to the regimen. Patients will be asked to record activities at least 3 days a week at the following times:

- Immediately after waking up in the morning
- 30 mins post medication use
- afternoon between 1200 - 1400 pm
- immediately before bedtime

Also, twice a week, patients will be asked to record during pre-identified activities that exacerbate pain (e.g. bending, climbing stairs, etc.). Patients will also be asked to wear a FitBit or similar activity monitor and upload their anonymized data (i.e. no personal health information shared).

Phase 1 – In-clinic sessions

In clinic sessions will also occur in Phase 1, occurring approximately every 3 weeks, taking the measures of VAS pain, VAS unpleasantness, C-SSRS, BDI/BAI, Neuropathic Pain Questionnaire, NIH PROMIS Global health and physical function scales and SF-36. Baseline LFP recordings will also be taken from ~2 minutes. At the study visits from week 3 onwards, we will also include

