A predictive biomarker of pain will be discovered in phase 1 from data collected with at-home and in-clinic recording sessions. This biomarker discovery will be implemented in Phase 2. In phase 1, if data of sufficiently high quality is collected before the 6-month phase period ends, and a predictive biomarker is found before the 6-month phase period ends, the patient can accelerate to the next phases of the study to help ensure a rapid positive clinical outcome.

Phase 2

In the first two weeks of Phase 2, patients will be seen daily for up to two weeks to optimize DBS parameters (visits 11-24), based on biomarker discovery from Phase 1. EEG may be used during this phase for safety, to ensure that subclinical seizure activity is not present during stimulation. If data-collection during the initial two-week period is curtailed for any reason, additional DBS optimization visits may be scheduled so as to sufficiently optimize the biomarker and stimulation settings to enable closed-loop stimulation.

Patients will then have closed-loop stimulation enabled for at-home stimulation, with follow-up clinic visits scheduled every 3 weeks. Stimulation will be enabled or disabled in an ON/OFF state with patient blinded to stimulation status to test for potential placebo / sham effects. In addition to at-home reporting (similar to Phase 1), efficacy of stimulation will be tested every three weeks in-clinic. Additional in-clinic testing of stimulation-related analgesia efficacy and mechanism of action will be done using acute administration of intranasal (4mg/0.1ml, up to two doses), intramuscular (0.4mg/1ml) or IV naloxone (0.4mg/1ml), or saline as control. Study team will assist in administering naloxone before and during analgesic stimulation ON/OFF. Patients and study team will be blinded to what is being provided. Patients who are participating in pain management using opioids will be excluded from performing this study procedure. Phase 2 will last approximately 6 months in duration, time period based on previous unpublished observations in human Parkinson's

patients from our group [143] and published non-human primate observations [58]. Phase 2 in-clinic visits occurring every 3 weeks will test the following:

- 1) VAS pain, VAS unpleasantness, C-SSRS, BDI/BAI, Neuropathic Pain Scale, NIH PROMIS Global health and physical function scales, and SF-36
- 2) Baseline LFP
- 3) Stimulation off + QST (no pain medication)
- 4) Stimulation on + QST (no pain medication)

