During this phase, patients will be monitored closely, with frequent at-home phone calls and in-clinic appointments. This phase of the study will last approximately 1 year (time line based on previous published reports [2, 85, 94], with in-clinic appointments occurring approximately every 6 weeks.

For the first two weeks of Phase 3, medical staff or researchers will contact patients on a daily basis to examine any changes in mood or pain symptoms. Clinic visits will also be scheduled every 6 weeks for 1 year, to examine pain and mood symptoms and routine follow-up care.

Conclusion of study: Formal data collection will be completed at 24 months post implantation. However, it is expected that patients will be followed for life in our clinic, as is the case for most patients implanted with DBS devices. At the end of the clinical trial, in consultation with patients' regular pain management teams, patients may be offered a potential therapeutic stimulation strategy (either open-loop or closed-loop), dependent on his or her pain alleviation from the clinical trial period. Patients will have the option to 1) continue active stimulation at the current setting with current device implantation, 2) continue stimulation but searching for a new setting, 3) discontinue stimulation (turning the device off) or 4) have the device removed. If patients opt to continue at-home active DBS after formal data collection has been completed, follow-up appointments will occur every 6 weeks.

The end of battery life for Activa PC+S is expected to occur 2-4 years after placement, depending on the chronic therapeutic stimulation parameters (similar to the sister device Activa PC that does not have a sensing function). The lead extender connecting the DBS leads to the pulse generator should not require replacement. When battery end of life occurs, it is expected that the Activa PC+S system will be removed, via the original chest incision, or replaced, dependent on further obtained approval based on the data collected in the present study and consultation with the regular pain management team.

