4.0 Clinical Measurements

Primary

Clinical ratings of pain will be measured by visual analog scales for pain as well as unpleasantness of pain sensation (i.e. “how much pain are you in right now?” and “how much is the pain bothering you right now?”). Patient reports of sensory and pain detection using the Quantitative sensory testing (QST) with the Medoc device will also be used, with and without stimulation.

Physiological measurements related to neural oscillatory activity during various triggered neural recordings with various pain states, activity states, medication states, etc. (~14 recordings per week at home, ~6-8 recordings per in-clinic visit,) will include: wide spectrum power-spectral analysis as well as using specific frequency domain for mean log power (i.e. in the delta, theta, alpha, beta, gamma bands), pain-related changes in broad spectrum power density, and coupling between the phase of low frequency rhythms and broadband gamma amplitude (phase-amplitude coupling, abbreviated PAC) [145-147].

Clinical measures and physiological measurements will be collected and recorded by members of the research and clinical team, as well as from at-home data collection sessions.

Secondary

Measures from Neuropathic Pain Questionnaire, Beck Depression and Anxiety, NIH PROMIS Global health and physical function scales and SF-36 will also be compared from pre-intervention to post Phase 1, phase 2 and phase 3 time points.

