6.0 Statistical Methods and Data Analysis

Ratings of pain will be measured by visual analog scales for pain as well as unpleasantness of pain sensation (i.e. “how much pain are you in right now?” and “how much is the pain bothering you right now?”). Patient reports of sensory and pain detection using the Quantitative sensory testing (QST) with the Medoc device will also be used, with and without stimulation.

In Phase 2, patients will serve as their own controls in a single-blinded phase (6-months in duration) in which placebo versus active open-loop stimulation is used. During this 6-month period, four sham and four active stimulation periods will occur in a random, blinded assignment. During the 8 in-clinic visits, the threshold for sensory and pain detection with the Medoc device will be used and scores will be compared for each patient during sham versus active stimulation periods in one-sample, two-tailed t-test. The 10 patients’ sham versus stimulation scores will also be used in group analysis to test the effects of open-loop and closed-loop stimulation.

In Phase 2, the visual analog scale scores recorded during the at-home recording sessions for various activities will be compared for each patient [(see Figure 3; 168 scores for sham sessions and 168 scores for active stimulation sessions, per patient); (i.e. 3 times per week for 4 activities and 2 times per week for at least 1 painful activity, for at least 14 VAS scores per week; 24 weeks total with 3 weeks per session-sham or stimulation, 8 sessions total, 4 sham sessions and 4 stimulation sessions)].

Multiple regression analysis of all patients will also be used to test for effects of stimulation on various activities, time of day, stimulation effects over time in trial and potential differences in stimulation effects on pain etiologies (i.e. spinal cord injury versus phantom limb versus post-stroke).

Phase 1 (no-intervention) VAS scores will be compared to Phase 2 (sham controlled and active stimulation) VAS scores.

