In Phase 3, patients will serve as their own controls in a single-blinded phase (12-months in duration) in which closed-loop versus active open-loop stimulation is used. During this 12-month period, ~four sham and ~four active stimulation periods will occur in a random, blinded assignment. During the ~8-9 in-clinic visits, the threshold for sensory and pain detection with the Medoc device will be used and scores will be compared for each patient during sham versus active stimulation periods in one-sample, two-tailed t-test. The 10 patients’ sham versus stimulation scores will also be used in group analysis to test the effects of open-loop and closed-loop stimulation.

In Phase 3, the visual analog scale scores recorded during the at-home recording sessions for various activities will be compared for each patient [(see Figure 3; ~364 scores for sham sessions and ~364 scores for active stimulation sessions, per patient); (i.e. ~3 times per week for 4 activities and 2 times per week for at least 1 painful activity, for at least ~14 VAS scores per week; ~52 weeks total with 6 weeks per session-sham or stimulation, ~8 sessions total, 4 sham sessions and 4 stimulation sessions)].

Multiple regression analysis of all patients will also be used to test for effects of stimulation on various activities, time of day, stimulation effects over time in trial and potential differences in stimulation effects on pain etiologies (i.e. spinal cord injury versus phantom limb versus post-stroke).

Phase 1 (no-intervention) and Phase 2 (sham controlled and open-loop stimulation) VAS scores will be compared to Phase 3 (open-loop stimulation and closed-loop) VAS scores.

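### Phases 2 and 3 name only the patient as blinded to stimulation state; the staff who run in-clinic QST, collect in-clinic VAS and phone patients are not said to be blinded

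*Combined protocol and SAP*

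**What the plan says.** Section 1.0 describes Phase 2 as follows: "Stimulation will be enabled or disabled in an ON/OFF state with patient blinded to stimulation status". Section 6.0 says of that phase that "patients will serve as their own controls in a single-blinded phase (6-months in duration", and uses the same single-blinded label for Phase 3. The synopsis describes Phase 3 as a comparison of "open-loop versus closed-loop stimulation parameters (single-blind study". Sections 1.0 and 3.0 name only patients as blinded to the Phase 3 strategy.

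On who measures, Section 4.0 says: "Clinical measures and physiological measurements will be collected and recorded by members of the research and clinical team", with at-home sessions as a further source. For the first two weeks of Phase 3, Section 3.0 says that "medical staff or researchers will contact patients on a daily basis to examine any changes in mood or pain symptoms". Daily calls are also listed for Phase 2 and elsewhere for Phase 3, without caller or content.

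For the naloxone-or-saline test within Phase 2, Section 1.0 says: "Patients and study team will be blinded to what is being provided".

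The activity monitor appears under the Phase 1 at-home recordings: "Patients will also be asked to wear a FitBit or similar activity monitor and upload their anonymized data". Section 6.0 plans no analysis of it.

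**The concern.** The synopsis lists pain VAS and thermal QST threshold as primary efficacy endpoints, and three questionnaires as secondary ones. All are patient reports. In QST the temperature ramps until the patient says that it is felt and then that it hurts, so the threshold depends on instruction, tone and prompting. A tester who knows the state and expects stimulation to work can shift it without intending to. The same applies to a VAS question put in clinic.

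The results carry weight. Showing therapeutic benefit is one of the criteria in Section 6.0 for a larger trial. Phase 3 is meant to show which mode works better for each patient, and the stimulation offered afterwards depends on pain relief in the trial. The research team may also move a patient early from Phase 2 to Phase 3, partly on pain relief. If observer influence favours active stimulation, or closed-loop over open-loop, it pushes all of these in the direction of the hypotheses.

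**Working it through.** **1. Who is blinded.** Every statement that names a blinded party for stimulation state names the patient (Sections 1.0 and 3.0, both phases). The single-blind labels in the synopsis and Section 6.0 agree. Section 6.0 also speaks of random, blinded assignment, and Section 3.0 of blinded randomization for visits 32-41, but neither says who is blinded. No QST operator, VAS collector, caller or analyst is named as blinded.

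**2. Which data are directly exposed.** QST and clinic VAS are collected with staff present. At-home VAS is entered by the patient in an online diary, by web or by text (Section 3.0). Section 6.0's count for it reproduces: 3 × 4 + 2 = 14 scores per week, and 14 × 12 weeks = 168 per condition in Phase 2. For Phase 3, 14 × 26 weeks = 364 per condition. Most VAS data therefore come without an interviewer.

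**3. Whether the visit list reveals the state.** The Phase 2 and 3 visit lists give QST with stimulation off, then QST with stimulation on. The synopsis requires a check of stimulation parameters at all study visits. Coding the period assignment alone would therefore not blind the tester.

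**4. What a bias would do (illustration).** From the documents: 10 patients, four sham and four active periods in Phase 2, two-tailed t-test. Assumed, because the documents give no value: 5% level, period SD 1, no true effect, a constant shift b favouring active, and a between-patient SD of the difference (τ) of 0 or 0.5.

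*Group paired t-test, 9 df.* Each patient's difference in means has variance 1/4 + 1/4 + τ² = 0.5 + τ². SE = √(0.5 + τ²)/√10, which is 0.2236 for τ = 0 and 0.2739 for τ = 0.5. The noncentrality is b/SE, and the false-positive rate is the two-sided noncentral t tail.

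| b (period SD) | Noncentrality, τ = 0 | False positive, τ = 0 | Noncentrality, τ = 0.5 | False positive, τ = 0.5 |
|---|---|---|---|---|
| 0.1 | 0.447 | 6.9% | 0.365 | 6.2% |
| 0.25 | 1.118 | 17.1% | 0.913 | 13.0% |
| 0.5 | 2.236 | 51.4% | 1.826 | 37.2% |

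*Single-patient test on four paired periods, 3 df.* SD of one paired difference = √2, and SE = √2/√4 = 0.707.

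| b (period SD) | Noncentrality | False positive |
|---|---|---|
| 0.1 | 0.141 | 5.1% |
| 0.25 | 0.354 | 5.8% |
| 0.5 | 0.707 | 8.1% |

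The single-patient rates are low because a test on four differences has little power to detect anything, bias included. Section 6.0 specifies a test within each patient but does not define the group analysis, so the group test here is a stand-in.

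**The case against.** The strongest reply is that single-blinding is declared openly, in a 10-patient pilot with no formal sample size and no significance threshold among its success criteria. That stands as a reason not to call this a fatal flaw. It does not remove the gap, because demonstrated benefit is one of those criteria.

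A reader might infer more than the documents support:

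- **That staff are known to be unblinded.** The documents are silent. They say who is blinded and name only the patient. If testers are already masked in practice, saying so closes much of the point.
- **That all VAS data are exposed.** Most are entered by the patient. Calls about pain are described only for the first two weeks of Phase 3; for Phase 2 that content would be an inference.
- **That nothing objective is compared by condition.** Section 4.0 lists neural measurements among the primary measures, and Section 6.0 compares LFP measures by DBS condition. They are not pain outcomes, but they are not self-report either.
- **That the monitor stops after Phase 1.** At-home reporting in Phases 2 and 3 is called similar to Phase 1, so continuation is unclear, not excluded.
- **That the naloxone test shows stimulation blinding to be feasible.** It masks the agent given. Stimulation ON/OFF in that same test is not said to be hidden from the team. It shows only that the plan accepts team-level masking during a clinic test.

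**Conclusion.** The point holds in this form: as written, the plan masks only the patient to stimulation state, and nothing protects the in-clinic QST and VAS comparisons from observer influence. At-home VAS is open to it only indirectly.

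The size is unknown. The range of about 6% to 51% belongs to a 10-patient paired test under an assumed shift of 0.1 to 0.5 period SD applied to the whole period mean, which is generous to the concern where diary scores dominate. For the within-patient test that Section 6.0 does specify, the same shifts give about 5% to 8%. Neither range shows that a positive result would be false. They show that a moderate shift, consistent across patients, could produce a positive pooled result with no true effect. The change is worth making before Phase 2 begins, but the gap does not invalidate the design.

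**What to change.** 1. **Separate the roles.** Hold the period assignment as a code known only to the existing team member who programs the device and does the stimulation-parameter check. Existing staff who run QST, collect VAS and make calls see only the period number until that phase's data are locked, with code break for safety. State who decides on early progression to Phase 3, and whether that decision is taken on coded data.
2. **Conceal the order within visits.** Replace the fixed off-then-on QST list with a random order set by the programmer and hidden from the tester. The list now places a stimulation-off wash-out after the on-state test. The amended text should say where that step falls in either order, so that its position does not reveal the state.
3. **Add an outcome not based on self-report.** State that the Phase 1 activity monitor continues through Phases 2 and 3, and compare mean daily activity between randomised periods as a secondary outcome, beside the LFP comparisons already planned.

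The cost is protocol wording and task allocation. The programmer and the tester must be different existing team members at a visit; the documents give no staffing numbers, so the site should confirm that this can be covered. Patients wear the monitor longer.

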- 5) Stimulation off + anticipatory anxiety task
- 6) Stimulation off + anticipatory anxiety task
- 7) Stimulation off + cognitive-attention task
- 8) Stimulation off + cognitive-attention task
- 9) Stimulation off + naloxone
- 10) Stimulation on + naloxone
- 11) Wash-out, stimulation off period
- 12) LFP recording after painful activity
- 13) Recording after pain medication

Phase 2 will test the effectiveness of closed-loop stimulation in comparison to no-stimulation. In phase 3, the effectiveness of closed-loop stimulation will be tested in comparison to open-loop stimulation settings. If data of sufficiently high quality are collected before the 6-month phase period ends in Phase 2, depending on pain relief symptoms, the research team may accelerate phase 2 to phase 3 before the 6-month period ends to ensure rapid positive clinical outcomes.

Phase 3

In phase 3, patients will continue with at-home stimulation with either personalized closed-loop or traditional open-loop stimulation strategies enacted via their implanted system. Patients will be blinded to the stimulation strategy in which they are assigned. Assignment of open-loop or closed-loop will be randomized and occur in 6-week time periods, with each patient serving as his or her control as to which stimulation treatment is more effective. EEG may be used during this phase for safety, to ensure that subclinical seizure activity is not present during stimulation.

During this phase, patients will be monitored closely, with daily at-home phone calls and frequent in-clinic appointments. This phase of the study will last approximately 1 year (time line based on previous published reports [2, 85, 94], with in-clinic appointments occurring approximately every 6 weeks.

In-clinic appointments will consist of the following:

- 1) VAS pain, VAS unpleasantness, C-SSRS, BDI/BAI, Neuropathic Pain Scale, NIH PROMIS Global health and physical function scales, and SF-36
- 2) Baseline LFP
- 3) Stimulation off + QST (no pain medication)
- 4) Stimulation on + QST
- 5) Stimulation off + anticipatory anxiety task
- 6) Stimulation on + anticipatory anxiety task
- 7) Stimulation off + cognitive-attention task
- 8) Stimulation off + cognitive-attention task
- 9) Stimulation off + naloxone
- 10) Stimulation on + naloxone

- 11) Wash-out, stimulation off period
- 12) LFP recording after painful activity
- 13) Recording after pain medication

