LFP data will be analyzed using wide spectrum power-spectral analysis as well as using specific frequency domain for mean log power (i.e. in the delta, theta, alpha, beta, gamma bands). We will also examine coherence and cross-frequency coupling between the channels [145-147]. Using a repeated measures ANOVA statistical analysis, summary statistics for power in relevant frequency bands, pain-related power changes, and indices of phase-amplitude coupling will be compared at different time points, different DBS conditions (on and off), possible medication states (on and off) and different pain states. Although the sample size is small, we will assess the correlation between pain and non-pain states with brain physiology measures, and clinical instruments used to measure pain relief produced by DBS. Additionally, bootstrapping statistical applications (i.e. a Monte Carlo algorithm) and general linear mixed models can be utilized to investigate potential statistical effects, given the small sample size.

Neural activity will be compared during pain states, activity states, medication states, etc. for Phase 1 (no-intervention), as well as Phase 2 (sham controlled and open-loop stimulation) and Phase 3 (open-loop stimulation and closed-loop stimulation).

Sample size calculation: This is a pilot study consisting of existing chronic brain recording technology. The goals are to provide pain relief strategies using the Activa PC+S neural interface, as well as assess feasibility and to collect data that will be used to inform treatment plans using DBS mechanisms. Thus, there is no formal sample size calculation. However, the study is designed such that patients will serve as their own controls in a blinded, placebo versus active open-loop stimulation design, with multiple periods of placebo versus active stimulation. Patients will also serve as their own controls in open-loop versus closed-loop stimulation, in a randomly assigned, blinded, multiple 6-week time periods of open-loop versus closed-loop stimulation. At-home recording sessions will also be utilized to increase the number of testing samples per patient over the trial. In this manner, the statistical power is increased to show treatment efficacy in either of these phases.

Criteria for study success that would justify a larger subsequent trial: This study will be considered to justify a larger subsequent trial if we can demonstrate that:

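### The Section 1.0 visit lists give no stimulation-on run for the cognitive task (Phases 2 and 3) or the anxiety task (Phase 2), so no within-visit on/off contrast can be formed for them

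*Combined protocol and SAP*

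**What the plan says.** Section 1.0 (Investigational Plan) has a numbered list of in-clinic tests for Phase 2 and another for Phase 3.

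- **Phase 2, anxiety task:** "5) Stimulation off + anticipatory anxiety task", followed by "6) Stimulation off + anticipatory anxiety task".
- **Phase 2 and Phase 3, cognitive task (same wording in both lists):** "7) Stimulation off + cognitive-attention task", followed by "8) Stimulation off + cognitive-attention task".
- **Phase 3, anxiety task:** an off run at item 5, followed by "6) Stimulation on + anticipatory anxiety task".

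The other paired tests in these lists change state between the two runs. QST is off at item 3 and on at item 4; the Phase 2 entry begins "4) Stimulation on + QST (no pain medication". Naloxone is off at item 9, followed in both lists by "10) Stimulation on + naloxone".

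The Phase 1 in-clinic text of Section 1.0 says that field potentials are recorded during both tasks. Section 6.0 (Statistical Methods and Data Analysis) plans to compare field-potential measures across "different DBS conditions (on and off", among other factors.

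**The concern.** An acute on-minus-off difference needs at least one run in each state. Two off runs at a visit can show practice effects or short-term repeatability, but not what stimulation does to reaction time, recall or the response to the anticipation cue. The same applies to the field potentials recorded during those runs.

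The surrounding entries suggest a copying slip. It still matters, because these lists are the only Phase 2 and Phase 3 instructions for the two tasks, and an on run that is not done at a visit cannot be recovered later.

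**Working it through.** The plan gives no figure of its own for these tasks: no sample size, power, effect size or named score analysis. The check is a count of runs, then of visits.

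**Runs per visit as listed in Section 1.0**

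| Test | Phase 2 off | Phase 2 on | Phase 3 off | Phase 3 on |
|---|---|---|---|---|
| QST (items 3-4) | 1 | 1 | 1 | 1 |
| Anxiety task (items 5-6) | 2 | 0 | 1 | 1 |
| Cognitive task (items 7-8) | 2 | 0 | 2 | 0 |
| Naloxone (items 9-10) | 1 | 1 | 1 | 1 |

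Three cells have no on run: the anxiety task in Phase 2 and the cognitive task in both phases.

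**Does another part of the plan supply the on run?** No. The Section 3.0 in-clinic lists for Phases 2 and 3 and the protocol chart mention neither task. The final research visit includes unnamed neuropsychological tests, but with no stimulation state and at one time point only.

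**Could off/off be a planned retest?** For the cognitive task this is unlikely. The Phase 1 in-clinic text already sets three consecutive trials per session to establish its reliability. No such trial count is given for the anxiety task, but no reason for a second off run is given either.

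**Visits on the planned schedule**

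- Phase 2: visits 25 to 31 give 31 − 25 + 1 = 7 (Section 3.0 and chart); Section 6.0 says 8.
- Phase 3: the chart says 8 to 10; Section 6.0 says about 8 to 9, which lies within that range.

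**Pairs without an on run, per patient** = (Phase 2 visits × 2 tasks) + (Phase 3 visits × 1 task)

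- Low: 7 × 2 + 8 = 22
- High: 8 × 2 + 10 = 26
- All 10 patients on the full schedule: 220 to 260

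The Nexus System Study text in Section 3.0 allows up to ten Phase 2 visits beyond the daily ones. If all ten were used, the ceiling would be 10 × 2 + 10 = 30. I use 7 to 8 because that is the planned schedule.

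**If the second run of each pair were on:** each patient would have 7 to 8 off/on pairs per task in Phase 2 and 8 to 10 for the cognitive task in Phase 3, against zero in each case now.

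**The case against.** The strongest reply is that this is a drafting slip with no bearing on any planned result. Neither task is a primary or secondary endpoint, Section 6.0 names no analysis of task scores, and the success criteria do not mention them. All of that stands, and it keeps the point minor.

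A second reply is that Section 3.0 and the chart hold the visit-by-visit schedule, and staff working from those would run neither task. This also stands. It means there are two discrepancies to settle: the stimulation state within Section 1.0, and the absence of both tasks from Section 3.0 and the chart.

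A reader might infer that no stimulation effect on attention, memory or anticipatory anxiety can be measured at all. The documents do not support that:

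- The Phase 3 anxiety task has an on run.
- Off-state results after different at-home periods (on versus off in Phase 2, open- versus closed-loop in Phase 3) could be compared in principle, although the plan describes no such analysis.
- A repeated off run is not worthless, since it gives within-visit repeatability.

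A reader might also infer that the field-potential comparison across stimulation states fails. It does not. Section 6.0 ties it to no particular task, and QST recordings are made in both states. Only the task-specific contrast is missing.

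Finally, the count of pairs measures how often one listing problem recurs. It is not a loss of power or precision.

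**Conclusion.** The point holds in a limited form. As listed, no acute within-visit on-versus-off contrast can be formed for the cognitive task in Phase 2 or Phase 3, or for the anxiety task in Phase 2, either in performance or in task recordings. The extent is about 22 to 26 pairs per patient. This assumes that the Section 1.0 lists are followed literally and that the patient completes the planned schedule. Early progression between phases, or a halt for the patient, lowers it.

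The Phase 3 anxiety task and the VAS and QST endpoints are unaffected. That the off/off entries are unintended is an inference from the neighbouring pairs; the documents do not say so. The point is minor, but worth correcting because the correction is cheap and the missed data are not recoverable.

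**What to change.** 1. Reconcile the two Section 1.0 lists. Either the second run of each affected pair (Phase 2 items 6 and 8, Phase 3 item 8) follows the off/on pairing used for QST, naloxone and the Phase 3 anxiety task, or a sentence states why off/off is intended. The first option is one word on each of three lines and adds no run; the second is one sentence.
2. Make the Section 3.0 in-clinic lists and the protocol chart agree with Section 1.0 on whether, and at which visits, the two tasks are done. This is a text change only.

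Randomising which state is tested first would separate practice from stimulation, but it is optional and not part of this correction. It would apply equally to the existing off-then-on pairs. It may also need added wash-out time: each list has a single in-visit wash-out, at item 11, with no stated length.
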